## 2. Study Objectives

### 2.1. PURPOSE OF STUDY

#### 2.2. PRIMARY OBJECTIVE

- To evaluate whether laparoscopic single anastomosis gastric bypass (LSAGB), laparoscopic Roux-en-Y gastric bypass (LRYGB) and laparoscopic sleeve gastrectomy (LSG) operations result in increased bile reflux, as determined by the presence of bile acids in the stomach and oesophagus, with or without stomach/oesophageal tissue damage

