##### **4.5.2. PRE-SURGICAL WORK UP**

- Participants will undergo the following investigations pre-operatively:
  - Endoscopy, including:
    - Gastric (+/- oesophageal) biopsies
    - Gastric aspirates for biochemical analysis
  - Blood testing

- Complete blood examination
- Serum levels of glucose and HbA1c
- Quantification of fasting lipids
- Weight and height will be measured for body mass index
  - Hip and waist circumference will also be measured to evaluate central obesity index

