#### 4.5.3. SURGERY

- Determination of the type of operation (LSAGB vs LSG vs LRYGB) to be performed will be at the discretion of the treating surgeon and informed patient preference.
- The operations will be performed by consultant oesophagogastric surgeons at the Royal Adelaide Hospital, The Queen Elizabeth Hospital, Western Hospital, Burnside War Memorial Hospital, Calvary Wakefield Hospital, Flinders Private Hospital or Ashford Hospital.

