# 7. Ethical Considerations

## 7.1. STUDY DESIGN

Although a prospective, randomized controlled trial would provide scientific rigour, we have elected to undertake a cohort study. Individual patient factors significantly impact the type of weight loss operation offered by surgeons, due to potential long-term morbidity, and thus clinical equipoise is lacking for randomization. Involvement in the study will not impact on the type of operation offered and investigator bias will be minimised through informed patient consent after in-depth discussion about available treatment options.

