## Statistical Analysis of data

- Statistical analysis will be undertaken for the primary outcomes relating to the three types of bariatric surgery being utilised in current clinical practice using commercially available statistical programs in consultation with professional statistical advice from our Unit's established connection with a health research statistician.
  - Normally distributed data will be reported as mean  $\pm$  standard error of the mean and statistical comparisons between groups will be made using parametric statistical tests.
  - Data that is not normally distributed, will be analysed using non-parametric statistics with reporting of median (interquartile range) and comparisons by applying non-parametric statistical tests with post-hoc analysis for differences across the 3 surgical groups.
  - Proportionate data will be compared using tests such as a Fisher's exact test or  $X^2$  test.
- The results will be presented at a relevant scientific forum and subsequently be submitted for publication in a peer-reviewed medical journal.

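### The operation is chosen on patient factors, but the tests named for proportions are unadjusted and the baseline reflux data have no role, so pre-existing differences can be read as an operation effect

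*Protocol*

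**What the plan says.** **Allocation.** Section 4.5.3 says that the type of operation "to be performed will be at the discretion of the treating surgeon and informed patient preference". Section 7.1 gives the reason for not randomising: "Individual patient factors significantly impact the type of weight loss operation offered by surgeons". The same section adds that "investigator bias will be minimised through informed patient consent after in-depth discussion about available treatment options".

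**Objective.** Section 2.2 asks whether the three "operations result in increased bile reflux, as determined by the presence of bile acids in the stomach and oesophagus". An increase implies a comparison with the state before surgery.

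**Analysis.** Section 9 (Statistical Analysis of data) says of normally distributed data that "statistical comparisons between groups will be made using parametric statistical tests". Other continuous data get non-parametric tests with post-hoc comparisons across the three groups. For proportions: "Proportionate data will be compared using tests such as a Fisher's exact test", or chi-square. It also refers to professional statistical advice.

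**Baseline data.** GerdQ is in the recruitment pack (4.5.1). The pre-surgical work-up (4.5.2) includes endoscopy with biopsies, "Gastric aspirates for biochemical analysis", and BMI. All are repeated at 6 months (4.5.5). The HIDA scan appears only in the 6-month list, and pre-operative impedance testing is selective (7.2).

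**The concern.** Where allocation follows patient characteristics, a crude difference between operations mixes the effect of the operation with the case mix of those who received it. The protocol itself says that the first condition is met. Background reflux is a plausible confounder: section 3.2 describes obesity as a risk factor for reflux and associates sleeve gastrectomy with more of it, so a surgeon might weigh existing reflux when choosing. That is an inference, not a statement in the protocol.

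The document names no method to separate the two components, although much of the information needed is already collected. Section 3.5 says that the results should inform surgical decisions about the safety of LSAGB. Confounding could either raise a false alarm about an operation or hide a real difference.

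**Working it through.** **1. The plan's own figure.** Inputs from section 4.4: 5% v 50%, power 80%, α = 0.05, Fisher's exact test, inflation factor 1.2, 10% for loss. Exact two-sided power by full enumeration is 77.7% at 16 per arm and 81.3% at 17, so 17 are needed. Then 17 × 1.2 = 20.4, rounded up to 21; 21 × 1.1 = 23.1, rounded up to 24; and 24 × 3 = 72. The stated 72 is reproduced, so the study is also sized on an unadjusted comparison.

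**2. Spurious difference with no operation effect.** Let q be the proportion of an arm with pre-existing reflux, r1 the 6-month risk with it and r0 the risk without it, both the same for every operation. The expected 6-month rate in an arm is p = r0 + (r1 − r0) × q. The spurious difference between arms A and B is (r1 − r0) × (qB − qA). All values of q, r1 and r0 are assumptions; the protocol gives none. I take r0 = 10%, r1 = 30% or 60%, and 22 evaluable per arm (24 less 10% is 21.6).

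| Baseline reflux, A v B | r1 | Expected rates, A v B | Spurious difference | Two-sided Fisher rejection |
|---|---|---|---|---|
| 20% v 50% | 30% | 14% v 20% | 6 points | 4.3% |
| 20% v 50% | 60% | 20% v 35% | 15 points | 12.5% |
| 10% v 60% | 30% | 12% v 22% | 10 points | 8.1% |
| 10% v 60% | 60% | 15% v 40% | 25 points | 35.0% |

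Worked example, last row: 0.10 + 0.50 × 0.10 = 0.15; 0.10 + 0.50 × 0.60 = 0.40; difference 0.25. With equal baseline prevalence and r1 = 60%, rejection is about 2.4%, because Fisher's test is conservative at this size. The largest spurious difference is 25/45 = 56% of the 45 points for which the study is sized.

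**3. Whether adjustment helps.** This was checked at 24 per arm, with r0 = 10%, r1 = 50% to 70% and no operation effect. Unadjusted Fisher rejects 6–10% at 20% v 40%, 19–36% at 10% v 50%, and 38–68% at 10% v 70%. A Mantel-Haenszel test stratified on baseline reflux (4,000 simulated runs each) rejects about 4–5% throughout. That is the favourable case, in which the confounder is measured without error; a proxy would remove less.

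**4. What the data can support.** Assume rates of 5%, 27.5% and 50%, where the middle one is the midpoint and is not in the protocol. Expected events are 22 × (0.05 + 0.275 + 0.50) = 18.15. Three operations need two indicator terms, so one or two covariates make three or four parameters, or 6.1 to 4.5 events per parameter. The lowest-rate arm has 22 × 0.05 = 1.1 expected events.

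**The case against.** **The bias is possible, not shown.** A reader might infer that baseline reflux differences will distort the result. The protocol does not support that: it speaks of individual patient factors and never says that reflux is among them. This stands, and the point is limited to what can happen.

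**The size depends on the assumed risks.** Nothing in the protocol supports a sixfold risk ratio between pre-operative and post-operative reflux once the anatomy has been altered, and GerdQ measures symptoms, not bile. With 30% v 10%, the 20% v 50% imbalance rejects only 4.3% of the time, below the nominal 5%. This stands too, so the range is shown. Even there, the estimated difference is off by 6 points.

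**Section 9 leaves room.** Its wording for proportions is by example, parametric tests could include analysis of covariance, and model details commonly belong to a statistical analysis plan. One may therefore say only that the protocol names no adjustment, not that it excludes one. But both tests it names for proportions are unadjusted, and the sample size rests on one of them.

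**The consent sentence may be misread.** A reader might take it as a claim that consent balances the groups. It refers to investigator bias and does not say that. It is nevertheless the only bias control that section 7.1 offers in place of randomisation.

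**Baseline data are incomplete.** HIDA, the first-listed primary outcome, has no pre-operative value. This limits the remedy for that outcome.

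**Conclusion.** The concern holds as a possibility that the stated analysis does not guard against. Allocation depends on patient factors by the protocol's own account, the tests named for proportions are unadjusted, and baseline reflux measures are collected without a role in the comparison.

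The amount of bias cannot be determined from the document. Under the assumptions shown, it runs from 6 points with rejection barely raised to 25 points with rejection of about one in three. A definite bias of any particular size is not supported.

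This should be fixed. The remedy uses data already planned, but it will reduce confounding, not remove it.

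**What to change.** In section 9:

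- Make the main between-operation comparison of each primary outcome adjusted for one or two baseline covariates named in advance: pre-operative aspirate bile acids, GerdQ, or both.
- For binary outcomes, use penalised (Firth) logistic regression, with Fisher's test as supportive.
- For aspirate bile-acid concentration and histology, use ANCOVA or rank-ANCOVA on the pre-operative value.
- State that scintigraphy has no pre-operative measurement and can be adjusted only for these proxies.
- Word conclusions as association.

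In section 7.1, state that informed consent does not control confounding between operation groups.

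**Cost.** Some extra analysis work, and no new patients, visits or tests. With about 18 expected events and three or four parameters, adjusted estimates will be imprecise, and residual confounding must be acknowledged in the report.

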# 10. Data and Biological Sample Storage

## 10.1. PARTICIPANT INFORMATION

- Personal data (name, contact details, etc.) will be recorded on the *Participant Details Form* (Appendix 3).
- Participants will be allocated individual numerical identifiers that will be used during the study for de-identification.
- The *Participant Details Forms* (Appendix 3) will be secured in a locked filing cabinet or similar, within the Department of Surgery at The Queen Elizabeth Hospital.

## 10.2. QUESTIONNAIRES

- Data from 'Reflux Symptom Score' and 'Investigation Tolerability' questionnaires will be stored electronically and kept securely on a password-protected computer in the Royal Adelaide Hospital. These data will also be backed up to a suitable secure CALHN device or server.
- Physical questionnaires will be secured in a locked filing cabinet or similar, within the Department of Surgery at The Queen Elizabeth Hospital.

## 10.3. BIOLOGICAL SAMPLES (BLOOD, TISSUE, BODILY FLUIDS)

- Samples will be stored in accordance with standard practice by and within SA Pathology.
- Data from laboratory analysis of blood, tissue and body fluid samples will be stored electronically and kept securely on a password-protected computer in the Royal Adelaide Hospital. These data will also be backed up to a suitable secure CALHN device or server.

## 12. Proposed Commencement / Duration

**Commencement Date:** February 2018

**Duration:**

- Patient recruitment: February 2018 – July 2020
- Patient follow-up: Six months after last operation is performed (around August 2020)

# 14. Appendices

Appendix 1: **Participant Information Sheet**

Appendix 2: **Participant Consent Form**

Appendix 3: **Participant Details Form**

Appendix 4: **GerdQ - Gastro-oesophageal reflux symptom questionnaire**

Appendix 5: **Investigation Tolerability Questionnaire**
